11.4 Analysis of Vital Signs and Weight

The following vital sign parameters will be obtained at each visit and summarized:

- Sitting systolic blood pressure (mmHg)
- Sitting diastolic blood pressure (mmHg)
- Sitting heart rate (or pulse) (bpm)
- Weight (kg)
- Height (cm)
- Body Mass Index (kg/m²)

- Respiratory rate (rpm)
- Body temperature (°C)

For continuous vital sign parameters, mean change from Baseline to minimum (smallest) value, maximum (largest) value, and final value in induction, maintenance, and during overall ADA exposure will be summarized. Subjects with potentially clinically significant results in induction, maintenance, and during overall ADA exposure will be identified according to the criteria in Table 6. Vital sign results meeting the criteria for potentially clinically significant findings will also be identified in a listing.

[figure not shown]
Table 6. Criteria for Potentially Clinically Significant Vital Sign Results

Vital Sign	Criterion	Definition of Potentially Clinically Significant
Systolic blood pressure	Low	Value ≤ 70 mmHg and decreased ≥ 20 mmHg from initial value
	High	Value $\geq 160 \text{ mmHg}$ and increased $\geq 20 \text{ mmHg}$ from initial value
Diastolic blood pressure	Low	Value \leq 50 mmHg and decreased \geq 15 mmHg from initial value
	High	Value $\geq 105 \text{ mmHg}$ and increased $\geq 15 \text{ mmHg}$ from initial value
Pulse	Low	Value \leq 50 bpm and decreased \geq 30 bpm from initial value
	High	Value ≥ 120 bpm and increased ≥ 30 bpm from initial value

12.0 Summary of Changes

Extensive changes have been made to this SAP based on design changes and agreements with the agencies on analyses of endpoints, based on Protocol Amendments 4 and 5. A high-level summary of changes:

- Reflect the final sample size of 93 subjects in the main study.
- Reflect the cessation of randomization to double-blind induction treatment, as well as the cessation of randomization to the internal placebo arm in the maintenance period per protocol Amendment 4.
- Reflect the resulting agreed changes to the analyses of endpoints as per protocol Amendment 5, including details on the sequentially rejective multiple test procedure and the final external placebo rates for confirmatory analyses.

• Addition of more detailed specifications and restructuring of content throughout the document.

13.0 References

Adalimum ab

M11-290 - Statistical Analysis Plan

Version 3.0 - 08 Aug 2019

Abbreviations

ADA Adalimumab

AE Adverse event

BMI Body mass index

CI Confidence Interval

CS Corticosteroid

CTC Common Toxicity Criteria

DB Double-blinded

DMARD Disease-modifying anti-rheumatic drug

DNA Deoxyribonucleic acid dsDNA Double-stranded DNA ECG Electrocardiogram every other week

ew every week

ESR Erythrocyte sedimentation rate

FMS Full mayo score

HACA Human anti-chimeric antibody hs-CRP High Sensitivity C-Reactive protein

IBD Inflammatory bowel disease

ICH International Conference on Harmonization
IDMC Independent Data Monitoring Committee

ITT Intent-to-treat

LOCF Last observation carried forward

MedDRA Medical Dictionary for Regulatory Activities

mITT Modified intent-to-treat

MTX Methotrexate

NRI Non-Responder imputation

NSAID Non-steroidal anti-inflammatory drug

OC Observed case
PK Pharmacokinetics
PMS Partial mayo score

PUCAI Pediatric Ulcerative Colitis Activity Index

RR Re-Randomized
SAE Serious adverse event
SAP Statistical analysis plan

SC Subcutaneous

Adalimumab M11-290 – Statistical Analysis Plan Version 3.0 – 08 Aug 2019

TB Tuberculosis

TNF Tumor necrosis factor UC Ulcerative Colitis

Addendum to Statistical Analysis Plan Version 3.0 (dated 08 August 2019)

Study M11-290

A Multicenter, Randomized, Double-Blind Study of the Human Anti-TNF Monoclonal Antibody Adalimumab in Pediatric Subjects with Moderate-to-Severe Ulcerative Colitis

Date: 03 March 2020

Introduction

This Addendum to the Statistical Analysis Plan Version 3.0 provides statistical details on additional sensitivity analyses as mentioned in Section 10.6 in the Statistical Analysis Plan.

Bayesian Sensitivity Analysis for the Second Co-Primary Endpoint

A Bayesian analysis as further described below was performed as sensitivity analysis for the primary analysis of the second co-primary endpoint (i.e., proportion of patients in clinical remission per Mayo score at Week 52 in Week 8 responders per partial Mayo score) of Study M11-290 (main, Ex-Japan) in order to take advantage of the number of N = 12 internal placebo patients and provide further insights into the difference in remission rates between Adalimumab and placebo taking into account prior anti-TNF experience status.

The Meta-Analytic Predictive (MAP) prior approach

A Bayesian meta-analytic approach was used to leverage information from available historical studies to generate a meta-analytic predictive (MAP) prior1 for the probability of remission in the placebo group. In this approach a Bayesian hierarchical normal prior structure was used on the logit scale probabilities of the remission rates under the exchangeability assumption. The resulting MAP prior on the logit scale was then back transformed to the original probability scale and expressed as mixtures of beta densities using the expectation maximization algorithm (EM).² This MAP prior, expressed as mixture of beta densities, was then used to obtain the corresponding posterior distribution by using the data from the placebo group of the current Study M11-290. Historical data from studies GEMINI 1³ and OCTAVE Sustain⁴ were used as the only available placebo-controlled multi-center Phase III studies (comparing against active treatment with Vedolizumab and Tofacitinib respectively) in adult patients with moderately to severely active UC with similar subject population (i.e., failure or intolerance to prior

corticosteroids or IMMs), study design (i.e., randomized withdrawal), and endpoint definition (i.e., remission per Mayo score at 1 year).

For the derivation of an informative prior for the remission rate in the Adalimumab group, data in the Adalimumab group from historical Study M06-827 was used. This study was the only available placebo controlled multi-center study (comparing against active treatment with Adalimumab) in anti-TNF experienced and naïve adult UC patients, with induction and maintenance phase and efficacy measured based on Mayo score remission at Week 52. Of note, Study M06-826 only had a double-blind randomized induction period and could therefore not be included in this sensitivity analysis. However, Study M06-827 did not use a randomized withdrawal design, therefore respective data from the placebo group could not be considered in the evaluation of the informative prior for the placebo group in addition to GEMINI 1 and OCTAVE Sustain Studies. The posterior distribution for the Adalimumab group was then obtained by using the data from the Adalimumab group of current Study M11-290.

Next, the posterior distribution on the difference (say, Delta) of the remission rates between Adalimumab and placebo was obtained from the respective posterior distributions of the remission rate in the placebo and Adalimumab groups, respectively using a convolution approach. Letting $x_1 \sim f_1(x)$ be the posterior density for the Adalimumab remission rates and $x_2 \sim f_2(x)$ the posterior density for the placebo remission rates, the difference $x \equiv x_1 - x_2$ is given by the following convolution: $f(x) = \int f_1(x) f_2(x-u) du = (f_1 * f_2)(x)$.

To take the prior anti-TNF experience status into account, this approach was applied separately for each stratum defined by the anti-TNF status (naïve and experienced) up to the point of obtaining the posterior distribution of Delta. After that the final posterior distribution of the difference in remission rates between Adalimumab and placebo was obtained by combining the two posterior distributions from anti-TNF experienced and naïve patients using the weights proportional to the sample sizes in the respective Adalimumab groups of Study M11-290.

As the final step, posterior probabilities for the difference in the remission rate (Delta) were evaluated for being greater than 0%, 10% and 15%. These posterior probabilities were evaluated for the combined dose groups ('M-HD/M-SD Combined'), the maintenance high dose group ('M-HD'), and the maintenance standard dose group ('M-SD').

Sensitivity analysis including robustification of priors

The additional analyses described below were performed as sensitivity analysis in order to further ensure the robustness of the main Bayesian approach described above. Here pooled data across anti-TNF experienced and naïve subjects from combined M-HD and M-SD doses was used. Considering the limited sample size in anti-TNF experienced subjects in Study M11-290, this pooled data approach seems to be the most appropriate to carry out a robust assessment of the main Bayesian analysis.

First, the MAP prior for the remission rates in placebo was obtained on the pooled data in a similar way as described above and was represented as mixture of beta densities. Next, in order to investigate the robustness of the MAP prior against discounting (i.e., reducing the impact of the informative prior) this prior was 'robustified' using two different approaches: a) adding the Jeffreys' prior as a non-informative mixing component with a weight of alpha with the MAP prior of weight of (1-alpha), hereafter referred to as rMAP prior⁶ and b) applying a tuning parameter tau to scale the beta parameters of each one of the component beta densities of the MAP prior, hereafter referred to as eMAP prior.⁷ These priors (MAP, rMAP, eMAP) for the placebo rate were then used to obtain respective posterior distributions using the pooled data from the placebo group in the current Study M11-290. Similar approach was adopted for the Adalimumab group where we started from an informative beta prior distribution and applied the same alpha and tau values to obtain priors with reduced information and subsequently obtained the corresponding posterior distributions. Hereafter these posteriors for both placebo and the Adalimumab groups were referred to as MAP posterior, rMAP posterior and eMAP posterior.

As a final step, the posterior probabilities for the difference between Adalimumab and placebo groups were evaluated for being greater than 0%, 10% and 15% under three different scenarios: i) with no discounting (alpha = 0 or tau = 1), ii) from derived rMAP posteriors with alpha = 0.20, iii) derived eMAP posteriors with tau = 1.25. Note that a value of alpha = 0.2 for the rMAP prior represents a 20% discounting and similarly a value tau = 1.25 in eMAP reduces the parameters of each beta component density by 20%.

Empirical checking of Data and Prior Conflict

To check if any obvious data-prior conflict was present in the analysis based on the MAP prior, an empirical approach was used by computing the marginal predictive probability of observing the currently observed responses in the placebo group using the above priors (rMAP, eMAP) for various values of alpha ($0 \le \text{alpha} < 1$) and tau (≥ 1). Note that for alpha = 0 the rMAP prior reduces to the MAP prior and similarly for tau = 1, eMAP prior becomes MAP prior. If there exists any obvious data-prior conflict which can be rectified by the rMAP or eMAP prior, then we would expect the marginal probability to increase for some choice of alpha > 0 (and tau > 1). A similar analysis was performed for the Adalimumab group.

Statistical Software

Analysis was implemented using R Studio (Version 1.1.453) and R statistical programming language (Version 3.5.1 64-bit) along with the following packages available on the Comprehensive R Archive Network (CRAN): "bayestestR," "Hmisc" and "RBesT." Outputs were generated using packages: "dplyr," "flextable," "purrr," "officer," "tibble" and "tidyr" available on CRAN.

References

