5.6 Discussion and Justification of Study Design

5.6.1 Discussion of Study Design and Choice of Control Groups

5.6.2 Appropriateness of Measurements

The design of this clinical trial was chosen to demonstrate adalimumab as an effective and safe therapy in pediatric subjects with moderately to severely active UC who failed conventional treatment. Prior to Amendment 4, at Baseline, subjects were stratified and randomized via the IVRS according to their Baseline disease severity, corticosteroid use at Baseline, and their prior exposure to anti-TNF to receive either one of the two induction

dose of adalimumab. For subjects who met the criteria for response per PMS at Week 8, the randomization was stratified by Week 8 remission status per PMS and Induction dose. After Amendment 4, subjects will receive open-label adalimumab high induction dose. At Week 8, subjects demonstrating a clinical response per PMS will be randomized 1:1 to one of two adalimumab maintenance treatment groups stratified by Week 8 remission status per PMS.

Since use of steroids and immunosuppressants are associated with significant adverse effects, subjects taking corticosteroid therapy at Baseline may have their corticosteroid therapy tapered based on the investigator's discretion starting at Week 4 and may have their immunosuppressants discontinued starting at Week 12.

Prior to Amendment 4, internal placebo was chosen as the control group during maintenance period per regulatory requirement. After Amendment 4, per agreement with the regulatory agencies, randomization to the internal placebo group will be ceased, and external placebo will be used as comparator for efficacy endpoints instead.

Standard statistical, clinical, and laboratory procedures will be utilized in this study. The clinical efficacy measurements in this study (Mayo Score and PUCAI) are commonly used for assessing disease activity in clinical studies in subjects with UC. All clinical and laboratory procedures in this study are standard or generally accepted.

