were to be randomized in a 2:2:1 ratio to one of two adalimumab maintenance treatment groups (standard dose [0.6 mg/kg (maximum dose of 40 mg) every other week (eow)] or high dose [0.6 mg/kg (maximum dose of 40 mg) every week (ew)]) or to placebo, respectively. The randomization was to be stratified by Week 8 remission status by PMS (defined as a PMS \leq 2 and no individual subscore > 1) and induction dose.

[figure not shown]
After Amendment 4, at Week 8, subjects demonstrating a clinical response per PMS (defined as a decrease in PMS \geq 2 points and \geq 30% from Baseline) were to be randomized and stratified by Week 8 remission status per PMS (defined as a PMS \leq 2 and no individual subscore > 1) in a 1:1 ratio to one of two adalimumab maintenance treatment groups (Standard dose [0.6 mg/kg (maximum dose of 40 mg) every other week] or High dose [0.6 mg/kg (maximum dose of 40 mg) every week]).

For blinding purposes, subjects received blinded treatment every week beginning at Week 8 and were to remain on double blinded therapy throughout the entire 52-week study as follows:

- Subjects randomized to standard dose were to receive a maintenance dose of 0.6 mg/kg (maximum dose of 40 mg) every other week and the matching placebo on the alternate week.
- Subjects randomized to high dose were to receive a maintenance dose of 0.6 mg/kg (maximum dose of 40 mg) ew.
- Subjects randomized to placebo prior to Amendment 4 were to receive matching placebo ew.

Ongoing subjects randomized prior to Amendment 4 were to continue their blinded treatment during the maintenance period until Week 52 and re-randomization to treatment for disease flare was to be done according to Amendment 3 stipulations in these subjects.

At Week 8, subjects who have not achieved a clinical response per PMS were to be discontinued from the study. A safety evaluation call was to be made 70 days after the

last dose of study drug administered to obtain follow-up information on any ongoing or new adverse events.

The duration of the study could be up to 66 weeks, which includes a Screening Period of up to 28 days, an 8-week double-blind induction period and a 44-week double-blind maintenance period and a 70-day follow-up. Upon completion of the study, subjects were to have the option to enroll into an open-label extension study where they were to continue to receive open-label adalimumab.

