4.3 Sample Size

[figure not shown]
The co-primary endpoints will be tested first for the combined high and standard adalimumab dose groups versus external placebo and then individual dose groups versus external placebo separately, controlling the familywise Type I error (multiple significance level) of 5% in a strong sense. For each individual test the nominal power will be calculated.

Assuming a 48% remission rate per PMS at Week 8 for the combined standard and high adalimumab induction dose groups and a remission rate per PMS of 19.83% for external placebo, a total of 77 subjects (presuming HD:SD = 46:31) in ITT-E population (see Section 5.1) provides at least 99% power for a one-sample two-sided Chi-square test using a significance level of 5%.

Assuming a 36% remission rate per Mayo Score at Week 52 for the combined standard and high maintenance dose groups and a remission rate per Mayo Score of 18.37% for external placebo, a total of 57 subjects (presuming HD:SD = 28:29) in the combined adalimumab maintenance dose groups in mITT-E population (see Section 5.1) provide 88% power for a one-sample two-sided Chi-square test using a significance level of 5%.

Assuming that the high adalimumab dose regimen is associated with higher efficacy than the standard adalimumab dose regimen and assuming a 52% remission rate per PMS at Week 8 for the high adalimumab induction dose group and a remission rate per PMS of 19.83% for external placebo, 46 subjects in the high adalimumab induction dose group of ITT-E population provide at least 99% power for a one-sample two-sided Chi-square test using a significance level of 4.95%.

Assuming a 41% remission rate per Mayo Score at Week 52 for the high adalimumab maintenance dose group and a remission rate per Mayo Score of 18.37% for external placebo, a total of 28 subjects in the high adalimumab maintenance dose group of the mITT-E population provide at least 80% power for a one-sample two-sided Chi-square test using a significance level of 4.95%.

Based on the assumption of a 75% response rate at Week 8, 93 subjects were to be included in the study (presuming 12 internal placebo subjects in the maintenance part of the study who were included prior to Amendment 4) to ensure 57 subjects in the combined adalimumab maintenance dose groups.

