5.0 Analysis Populations

5.1 Definition for Analysis Populations

Seven study populations will be used for analyses in this study. These are:

[figure not shown]
Intent-To-Treat (ITT) population: The ITT population includes all subjects who received at least one dose of the study medication during induction period. ITT subjects will be analyzed as randomized/enrolled.

ITT-E population: The ITT-E population will be a subpopulation of the ITT population, where subjects who have received open-label high induction dose will be excluded. The ITT-E is the primary population for the confirmatory induction period efficacy analyses.

Modified ITT (mITT) population: The mITT population consists of all Week 8 PMS responders who were randomized at Week 8 and received at least one dose of the study medication during maintenance period. mITT subjects will be analyzed as randomized at the beginning of maintenance phase.

mITT-E population: The mITT-E population will be a subpopulation of the mITT population, where subjects who have received Placebo will be excluded. The mITT-E is the primary population for the confirmatory maintenance period efficacy analyses.

Re-Randomized (RR) population: Consists of all subjects who were re-randomized due to a disease flare and received at least one dose of the study medication after the re-

randomization. RR subjects will be analyzed as randomized at the beginning of maintenance phase.

[figure not shown]
Safety population: Includes all subjects who received at least one dose of the study drug. The safety population will be analyzed (separately for induction and maintenance phase) as treated, according to treatment the subject actually received. The safety population will be used for safety analyses.

Per Protocol (PP) populations: The PP populations will only be used for sensitivity analyses of the co-primary and ranked secondary endpoints.

- The I-PP population is a subset of the ITT-E population/mITT-E population consisting of subjects without major protocol deviations within the induction period.
- The M-PP population is a subset of the mITT-E population consisting of subjects without major protocol deviations throughout the study.

The following treatment groups will be distinguished for ITT [ITT-E will comprise only I-HD and I-SD], mITT [mITT-E will comprise only M-HD and M-SD], safety and RR population:

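### The Addendum's Bayesian adalimumab-minus-placebo difference is partly non-concurrent: its adalimumab data are not restricted to children who could have been allocated placebo

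*SAP*

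**What the plan says.** Before Amendment 4, Week 8 responders "were to be randomized in a 2:2:1 ratio to one of two adalimumab maintenance treatment groups" or to placebo, stratified by Week 8 remission status and induction dose (SAP 4.2). After Amendment 4, all new children received open-label high-dose induction, and responders were randomized "in a 1:1 ratio to one of two adalimumab maintenance treatment groups", stratified by Week 8 remission status only. Protocol 5.6.2 records the change: "randomization to the internal placebo group will be ceased, and external placebo will be used as comparator for efficacy endpoints instead".

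SAP 5.1 does not separate the two periods in maintenance: "The mITT population consists of all Week 8 PMS responders who were randomized at Week 8". The M-HD and M-SD groups are defined by dose, not by when the child was randomized.

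The SAP Addendum (03 March 2020) adds a Bayesian sensitivity analysis for the second co-primary endpoint, "in order to take advantage of the number of N = 12 internal placebo patients". The placebo arm combines those children with a prior built from GEMINI 1 and OCTAVE Sustain. The adalimumab arm has a prior from adult Study M06-827, and then: "The posterior distribution for the Adalimumab group was then obtained by using the data from the Adalimumab group of current Study M11-290". Delta is evaluated for M-HD, M-SD and both combined. The analysis is stratified only by prior anti-TNF status, and the strata are combined with weights proportional to the adalimumab sample sizes.

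**The concern.** The particular value of the internal placebo arm is that it was randomized alongside adalimumab within this trial. Setting it against an adalimumab group that includes later children gives up part of that value, because calendar time and induction regimen can then enter Delta.

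The plan itself treats the later children as different. ITT-E excludes them from the confirmatory Week 8 analysis. Week 8 randomization was stratified by induction dose while two doses were in use. SAP 10.7 lists I-HD-OL as a separate induction subgroup for Week 52 remission. Entry to maintenance also depends on the Partial Mayo Score, which contains the physician's global assessment. After Amendment 4 that rating was made knowing that the child had received high-dose induction, so selection at Week 8 may differ between periods.

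The Addendum's robustness steps (rMAP with alpha = 0.20, eMAP with tau = 1.25, and the data-prior conflict check) all concern the historical priors. None addresses non-concurrency within the trial's own data.

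**Working it through.** All counts below are planning figures. The Addendum gives no adalimumab N.

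**Inputs** (SAP 4.3 unless noted)
- 93 children in total and a 75% Week 8 response rate.
- 12 internal placebo and 57 combined adalimumab children in maintenance.
- "a total of 77 subjects (presuming HD:SD = 46:31) in ITT-E population", which excludes open-label induction (SAP 5.1).
- Assumed Week 52 remission of 36% on adalimumab and 18.37% on external placebo.
- Week 8 ratios of 2:2:1, then 1:1 (SAP 4.2).

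**The plan's own figures**
- 93 × 0.75 − 12 = 57.75, against 57 stated.
- One-sample power at n = 57, normal approximation: Φ[(0.1763 × √57 − 1.96 × √(0.1837 × 0.8163)) / √(0.36 × 0.64)] = 88.3%, against 88% stated.

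**Split by period**
- Before Amendment 4: 77 × 0.75 = 57.75 responders. One fifth is 11.55 placebo, matching the planned 12. Four fifths is 46.2 adalimumab.
- After Amendment 4: (93 − 77) × 0.75 = 16 × 0.75 = 12 responders, all on adalimumab.
- Non-concurrent share by this route: 12/57 = 21%.
- Working instead from the placebo count, 4 × 12 = 48 concurrent adalimumab children, leaving 57 − 48 = 9, or 9/57 = 16%.

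**Induction imbalance**
- High-dose induction in the placebo arm: 46/77 = 60%.
- In the pooled adalimumab group: (46.2 × 46/77 + 12) / (46.2 + 12) = 39.6/58.2 = 68%.

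**Effect on Delta**
- Shift in the data part = non-concurrent share × difference in remission between later and concurrent children. The documents give no such difference; 10 to 20 points is an assumption.
- Lower end: 9/57 × 10 = 1.6 points. Upper end: 12/57 × 20 = 4.2 points.
- The M06-827 prior dilutes this. Its weight is not stated. If it were worth 50 to 250 children (an assumption), 12 later children would move the adalimumab posterior mean by 12/107 to 12/307 of the difference. That is 1.1 to 2.2 points at the lighter prior and 0.4 to 0.8 at the heavier.

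**Cost in precision of restricting** (no borrowing)
- n = 57 against 12: √(0.36 × 0.64/57 + 0.1837 × 0.8163/12) = 0.129.
- n = 45 (57 − 12) against 12: √(0.36 × 0.64/45 + 0.1837 × 0.8163/12) = 0.133, about 3% larger. The 12 placebo children dominate the variance.
- 95% half-width of the restricted estimate: 1.96 × 0.133 = 26 points.

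**The case against.** The strongest reply is that this is a sensitivity analysis of one endpoint. The confirmatory tests compare mITT-E with fixed external rates, so nothing here can change them. Maintenance was blinded in both periods, entry required the same response, and allocation was stratified by Week 8 remission throughout. SAP 10.7 already plans Week 52 Mayo remission by I-HD, I-SD and I-HD-OL in the mITT set, which includes placebo, so the component rates will be on display. All of this stands and limits the consequence. It does not put the concurrent comparison into Delta, and no concurrent difference is planned.

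A reader might also infer more than the documents support:
- **That this is the only use of the internal placebo arm.** It is not. SAP 10.1 reports Week 52 endpoints by treatment group with 95% CIs on mITT, and placebo also appears in the safety summaries. It is the only planned efficacy contrast.
- **That Delta is wholly non-randomized because of the later children.** On planning figures about 79% to 84% of the adalimumab group was randomized while placebo was open.
- **That restricting the adalimumab group would make Delta a randomized comparison.** Both arms would still carry adult historical priors. Only the unborrowed concurrent difference is randomized.
- **That 0%, 10% and 15% are decision thresholds that the shift might cross.** The Addendum evaluates posterior probabilities at these values and attaches no success rule.

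**Conclusion.** The point holds as a cheap improvement to a sensitivity analysis. Delta, the only planned efficacy contrast with internal placebo, is partly non-concurrent as well as prior-augmented, and nothing in the Addendum separates the two periods. The likely size is modest: 16% to 21% of the adalimumab data, and a shift of about 1.6 to 4.2 points in the data part of Delta before the adalimumab prior reduces it.

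This rests on three things. Inclusion of the later children is inferred from the absence of a restriction, not from an explicit statement. The counts are planning figures. The 10 to 20 point difference is assumed. The documents also do not say which Week 8 ratio applied to children still in blinded induction when Amendment 4 took effect, so the non-concurrent share could be larger than 21%.

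**What to change.** 1. Report the adalimumab N by enrollment period, and by the Week 8 ratio under which each child was randomized.
2. Re-run Delta with the current-study data in all arms restricted to children randomized 2:2:1 at Week 8, and show the all-children version alongside.
3. Add the unborrowed concurrent adalimumab-minus-placebo difference with its 95% CI, presented as an estimate and not a test. Account where feasible for both Week 8 randomization factors, remission status and induction dose; with 12 placebo children the strata will be thin. Cross-reference the SAP 10.7 induction-group table.
4. Describe the existing Delta as partly non-concurrent and prior-augmented.

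The cost is one re-run sensitivity analysis, with data-only intervals about 3% wider, and no new data. The unborrowed estimate will be imprecise, with a 95% half-width of about 26 points, and should be reported with that caveat.

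### The SAP Addendum's formula for the adalimumab-minus-placebo difference is not the density of a difference; followed as printed, it makes the posterior probability of any benefit equal to 1

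*SAP*

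**What the plan says.** The Addendum describes a Bayesian sensitivity analysis of the second co-primary endpoint (Mayo remission at Week 52 in Week 8 responders), added to "take advantage of the number of N = 12 internal placebo patients".

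In its section on the Meta-Analytic Predictive (MAP) prior approach, f1 is said to "be the posterior density for the Adalimumab remission rates" and f2 is "the posterior density for the placebo remission rates". The target is the difference x = x1 - x2, which "is given by the following convolution". The display then runs "f_1(x) f_2(x-u) du = (f_1 * f_2)(x" (the quote stops before the closing bracket). No minus sign is attached to x2, and f2 is not redefined as the density of -x2.

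The step is applied within each anti-TNF stratum, the strata are combined, and then "posterior probabilities for the difference in the remission rate (Delta) were evaluated for being greater than 0%, 10% and 15" percent, for the combined, high-dose and standard-dose maintenance groups. The robustness section that follows uses the same thresholds for the same difference and gives no other formula.

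**The concern.** The convolution of two densities is the density of the sum of two independent variables. The line therefore describes a different quantity from the one it defines, and nothing elsewhere in the Addendum corrects it.

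This is the only stated rule for getting from the two arm-level posteriors to Delta. Among the analyses specified for this endpoint, this one uses the study's own placebo subjects to estimate a treatment difference; the confirmatory tests compare with fixed external rates. If the printed rule were coded, the probability of any benefit would carry no information, and the 10% and 15% probabilities could look decisive with no effect at all.

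**Working it through.** **Is there a plan figure to reproduce?** The Addendum prints no posterior probability and no fitted prior, so there is none for this step. The design inputs for the same endpoint do reproduce. SAP section 4.3 has n = 57, 18.37% versus 36%, two-sided 5%:

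- null SE = √(0.1837 × 0.8163 / 57) = 0.0513
- alternative SE = √(0.36 × 0.64 / 57) = 0.0636
- power = Φ[(0.1763 - 1.96 × 0.0513) / 0.0636] = Φ(1.19) = 88.3%, against a stated 88%.

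**Step 1: what each expression is.**

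- Sum, x1 + x2: ∫ f1(u) f2(x - u) du, which is what `(f1 * f2)(x)` denotes.
- Difference, x1 - x2: ∫ f1(u) f2(u - x) du, which is f1 convolved with the density of -x2.
- Integral as typed: ∫ f1(x) f2(x - u) du. Here f1(x) does not depend on u and comes outside. The rest integrates to 1, leaving f1(x).

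The typed integral and the closing expression therefore disagree with each other, and neither is the difference.

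**Step 2: the 0% threshold.** Both rates lie between 0 and 1. The sum x1 + x2 and the rate x1 are both positive with probability 1, so P(> 0) = 1 whatever the data. Combining the two strata cannot change this, because each stratum has no mass below zero.

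**Step 3: the 10% and 15% thresholds.**

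Inputs from the documents:

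- 57 adalimumab subjects: "a total of 57 subjects (presuming HD:SD = 28:29") in SAP section 4.3
- 12 internal placebo subjects: Addendum
- 36% and 18.37%: SAP section 4.3

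Assumption: Jeffreys Beta(0.5, 0.5) in each arm, without stratification. The Addendum names Jeffreys only as a mixing component, so this is an illustration and not its analysis.

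For example, at equal 18.37% rates:

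- adalimumab: 0.1837 × 57 = 10.47, giving Beta(10.97, 47.03)
- placebo: 0.1837 × 12 = 2.20, giving Beta(2.70, 10.30)

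Each cell gives P(> 0) / P(> 10%) / P(> 15%):

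| Adalimumab vs placebo | Correct, x1 - x2 | Sum reading | Typed integral, f1 |
|---|---|---|---|
| 36% vs 18.37% | 0.88 / 0.69 / 0.55 | 1 / 1.00 / 1.00 | 1 / 1.00 / 1.00 |
| 18.37% vs 18.37% | 0.48 / 0.16 / 0.06 | 1 / 1.00 / 0.997 | 1 / 0.975 / 0.77 |
| 20% vs 50% | 0.02 / 0.002 / 0.000 | 1 / 1.00 / 1.00 | 1 / 0.99 / 0.85 |
| 5/57 vs 1/12 | 0.47 / 0.06 / 0.01 | 1 / 0.92 / 0.71 | 1 / 0.40 / 0.09 |
| 0/57 vs 0/12 | 0.28 / 0.000 / 0.000 | 1 / 0.13 / 0.055 | 1 / 0.001 / 0.000 |

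**Step 4: how far this depends on the priors.** Now assume a tighter placebo posterior, Beta(22.7, 100.3), with mean 22.7/123 = 18.5%.

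- Adalimumab at 36% of 57: correct values 0.995 / 0.86 / 0.65; sum reading 1.00 throughout.
- Adalimumab at 18% of 57: correct values 0.49 / 0.06 / 0.01; sum reading 1.00 throughout; typed integral 1 / 0.97 / 0.75.
- Adalimumab at 36% with a placebo mean of 12% and the same effective size: correct values 1.00 / 0.98 / 0.91.

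The last case matters because 18.37% is an upper 95% confidence limit and not a central estimate. With a lower placebo rate and a real effect, the correct and misprinted answers come close. They separate most when the effect is absent or reversed.

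**The case against.** The best defence is that this is a notation slip. The prose says difference throughout the Addendum, and x1 - x2 is written out immediately before the display. The typed integrand cannot be run as a convolution at all, so it reads as loose description and not as code. A difference posterior with no mass below zero would also be conspicuous in output. The text was read from a PDF, so the x in place of u inside f1 could be an extraction artefact.

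Most of this stands as a limit on the consequences. It does not rescue the line: repairing the u/x slip still leaves f2(x - u) and the closing `(f1 * f2)(x)`, and both point to the sum.

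Three stronger readings are tempting, and the documents support none of them:

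- **That all three probabilities are near 1 whatever the data show.** This is exact only at 0%. At 10% and 15% it fails when both rates are low (0.92 and 0.71 on the sum reading for 5/57 versus 1/12), and it fails on the typed integral at lower adalimumab rates.
- **That results already produced are wrong.** The Addendum describes an analysis already run in R, but it gives package names only, with no code, fitted priors or results.
- **That the trial's main conclusion is at risk.** The confirmatory decision rests on the one-sample chi-square tests in SAP sections 10.1 and 10.5, which do not use this formula.

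**Conclusion.** The printed formula is wrong for the quantity it defines, and no reading of the line yields the difference. P(Delta > 0) = 1 follows from the support of the two rates and needs no assumption about priors or data.

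The size at 10% and 15% is illustrative. It rests on assumed Jeffreys priors, unstratified data and 57 versus 12 subjects. With equal 18.37% rates, 0.16 and 0.06 become 1.00 and 0.997 (sum) or 0.975 and 0.77 (typed integral). The inflation is much smaller when both rates are very low.

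Whether the error goes beyond the printed page cannot be settled from the documents. It is confined to a sensitivity analysis of one co-primary endpoint. It should still be corrected, because a reader cannot tell which quantity the posterior probabilities describe.

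**What to change.** In the Addendum's MAP section, replace the display with f(x) = ∫ f1(u) f2(u - x) du, and state that this is f1 convolved with the density of -x2. Confirm from the executed R code that x1 - x2 was computed in each anti-TNF stratum and in the pooled MAP, rMAP and eMAP analyses. One quick check is that the posterior for Delta can take negative values. If the code followed the printed line, re-run the 0%, 10% and 15% probabilities for the combined, high-dose and standard-dose groups.

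The cost is one corrected line and a code check of minutes, plus a re-run only if the check fails. The confirmatory analysis does not change.
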